
Research Procedures
	
 • The primary research procedures for Aims 1, 2 and 3A are a retrospective review of blood pressure levels for outpatients in the Cedars-Sinai system before and after the introduction of the new clinical guidelines. • Aim 3B is a pilot study to assess the use of home blood pressure monitoring linked to the electronic medical record. This is a prospective intervention of an already approved device, which is compatible with the Cedars-Sinai electronic medical record system and promoted on the Cedars-Sinai website. Study participants for this feasibility study will only include patients already under the care of the PI. • Aim 4A involves conducting interviews discussions to understand the feasibility and implementation of an intervention to increase medication adherence. Participants in the interviews will include current patients who are taking hypertension medications as well as clinic staff. • Aim 4B is a pilot study to evaluate the feasibility, acceptability, and efficacy of an intervention to increase medication adherence involving text message reminders and small incentives for adherence to pill-taking routines.

Subject Population
	
 • For Aims 1-3: All patients seen at least twice in a 12-month period at any Cedars-Sinai outpatient facility • For Aim 4A: All patients with hypertension currently taking hypertension medication and clinic staff • For Aim 4B: All patients with hypertension taking hypertension medication

Duration	
 • For Aims 1, 2 and 3A, all data is retrospective, using already available data collected during routine care. The data to be utilized was collected as part of clinical care from 1/1/2012 through 3/30/2019. • For Aim 3B, prospective data collection will occur during a 9 week period, beginning at the time of patient enrollment. • For Aim 4A, interviews will last one hour on regular clinic days. • For Aim 4B, prospective data collection will occur during a 9 month period, beginning at the time of patient enrollment.
----------	--

GENERAL INFORMATION

CSMC Co-Investigators	
[name], MS [name]
 
[name] [name]

Sponsor/Funder	NIH/NHLBI
Collaborating Institutions Involved in the Research	
RAND Corporation [name]

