1.0 BACKGROUND, RATIONALE

Routine ambulatory care visits with diverse clinical specialists represent critical missed opportunities to identify and treat patients with undiagnosed or under-treated hypertension. Hypertension is one of the most important cardiovascular risk factors in both its prevalence and the severity of its consequences.¹ Decades of laboratory and clinical studies have demonstrated a clear link between hypertension and devastating cardiovascular events including stroke, myocardial infarction and renal failure.²⁻⁸ Despite the clear risk, half of hypertensive individuals have blood pressures that exceed current standards for control (<130/80), including nearly 20% of hypertensive individuals who have not yet been given a diagnosis.^{1,9} The high rates of undiagnosed and uncontrolled hypertension appear largely due to lack of recognition or insufficient action by clinicians and health systems, rather than lack of access to care: 82% of individuals with uncontrolled hypertension have a routine place of care and nearly two thirds had at least two ambulatory care visits in the past year.¹⁰ Blood pressure is routinely documented during most ambulatory visits, even in specialty clinics like ophthalmology and orthopedics. Moreover, electronic medical record systems (EMRs) have been widely adopted in outpatient clinics,¹¹ and EMR data that is routinely recorded during clinical encounters can accurately identify patients with undiagnosed or uncontrolled hypertension.¹²⁻¹⁶ This means that health systems already have the data and technical expertise needed to identify patients with undiagnosed and undertreated hypertension. However, few health systems leverage these resources, probably because the feasibility and benefits of doing so have not been demonstrated.

As such, our proposed research program will leverage the capabilities of the EMR to in the detection and treatment of uncontrolled hypertension. Via a future NHLBI-funded K23 Career Development Award, we will achieve two long-term goals. First, we will demonstrate how health systems can use the EMR for the surveillance and detection of undiagnosed and under-treated hypertension. Second, we will develop and test health system-based interventions aimed at reducing the time that hypertensive patients spend without a diagnosis, intensified treatment, or optimal control. We plan to use

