2.0 STUDY OBJECTIVES

The objective of the currently proposed study is to provide pilot data for this longer-term research program. In preparation for this K23 application, we must achieve the following aims.

Aim 1: Determine the cross-sectional prevalence of undiagnosed and uncontrolled hypertension within the Cedars-Sinai Health System, as well as the patient, physician, and clinic characteristics associated with these outcomes. This will document the presence and extent of problems at this institution and reveal which populations and settings are most affected, providing insights that can be used to develop and implement future interventions.

Aim 2: Develop and pilot test new time-to-care and time-to-control measures. These measures will evaluate (1) how long it takes from when evidence exists in the EMR that patients meet criteria for hypertension before clinicians document a diagnosis and initiate treatment, (2) how long evidence exists that control is suboptimal before clinicians intensify treatment, and (3) how long each of these conditions exists before goal blood pressures are achieved. We plan to use these new measures in our future work because we expect them to be more responsive to changes in care than cross-sectional measures of control would be, and because they include both care processes (i.e., did clinicians do the right things) and outcomes (i.e., were clinical goals achieved), making it possible to distinguish whether suboptimal control is due lack of recognition, lack of action (e.g., clinical inertia), or insufficient action (e.g., suboptimal adjustment of antihypertensive medications).

Aims 3A and 3B: Aim 3A – Assess the validity, responsiveness, and potential utility of the new time-to-care and time-to-control measures. To assess validity, we can examine whether performance on the new measures is associated with performance on cross-sectional measures of blood pressure control. To assess responsiveness and potential utility, we can examine how performance changes with clinical practice. For example, the introduction of the 2017 ACC/AHA guidelines represented a marked change in the standard of care for hypertension in terms of criteria for diagnosis and blood pressure goals. If the

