4.0 STUDY DESIGN AND METHODS

Achieving these objectives and aims will involve an analysis of existing data from ambulatory care visits at clinics affiliated with Cedars-Sinai Medical Center from January 1, 2014 through March 30, 2019. Via a detailed study protocol, we will establish patient eligibility criteria, specify study variables and measures for extraction from the EMR, and specify descriptive and multivariate regression analyses

related to Aims 1-3. An Advisory Board consisting of local and national experts in EMR systems, population health, hypertension, and the implementation of quality improvement interventions will provide guidance and feedback on the protocol and after we have obtained preliminary data.

Patients will need to have at least two years of data available in CS-Link to be included in the study (defined as two or more clinic visits at least two years apart and occurring within the study dates). We will include ambulatory care visits with faculty, medical delivery network, and private physicians in all specialties if they use CS-Link. We will exclude care in the emergency department, urgent care, and hospital settings because blood pressure may be temporarily elevated due to acute illness. For eligible visits, we will obtain the recorded blood pressure values, whether the blood pressure was assessed manually or automatically (if available), and the physician identity (coded).

We will define blood pressure control based on the 2017 ACC/AHA guidelines (blood pressure <130/80). In sensitivity analyses, we will also consider control based on the JNC-7 guidelines (blood pressure <140/90), due to the recent change in the standard of care.

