7.0 STATISTICAL CONSIDERATIONS

7.1 STUDY OUTCOME MEASURES

Analyses will test the following pre-specified hypotheses for each goal:

Aim	Hypotheses
1: Determine cross-sectional prevalence of undiagnosed and uncontrolled hypertension at CSMC, as well as the patient, physician, and clinic characteristics associated with these outcomes.	
 1) Cross-sectional rates of undiagnosed and uncontrolled hypertension at CSMC, based on the 2017 AA/AHA Guidelines, will be similar to national rates (20% and 50%, respectively). 2) Cross-sectional rates of undiagnosed and uncontrolled hypertension will be higher under the 2017 ACC/AHA Guidelines than the JNC-7 Guidelines. 3) Rates of undiagnosed and uncontrolled hypertension will be lower among patients with visits in Primary Care, Internal Medicine, Nephrology, or Cardiology clinics than for patients who only receive care in other clinics.
2: Develop and pilot test new time-to-care and time-to-control measures.	
 1) Data already collected in the EMR can be used to calculate these five new measures of hypertension care.
3A: Assess the validity, responsiveness, and potential utility of the new time-to-care and time-to-control measures.	
 1) Performance on the time-to-care and time-to-control measures will be associated with cross-sectional control rates at the clinic and physician level. 2) Following release of the 2017 ACC/AHA Hypertension Guidelines, performance on the time-to-control measures and cross-sectional control rates will worsen while performance on time-to-care measures will remain stable. 3) Performance on the time-to-care and time-to-control measures will be better for patients with visits in Primary Care, Internal Medicine, Nephrology, and Cardiology clinics than for patients who only receive care in other clinics.

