Aim 3B: Pilot study of the new time-to-control measure's responsiveness to more intensive blood pressure monitoring and intervention	
 1) Use of home blood pressure monitors linked the EMR will allow for weekly intervention by a clinical pharmacist, with titration of antihypertensive therapy, according the to 2017 ACC/AHA Hypertension Guidelines 2) The time-to-control period with will be shorter for those enrolled in the pilot study than those in the general population, not provided with home monitoring and weekly clinical pharmacist intervention
Aim 4A: Interview discussions to explore feasibility and acceptability intervention to increase blood pressure medication adherence	
 1) This is an exploratory aim, designed to inform Aim 4B. No a prior hypothesis.
Aim 4B: pilot study to measure the feasibility, acceptability, and efficacy of interventions designed to increase blood pressure medication adherence	
 1) Medication adherence and hypertension control will be greater among treatment groups compared to control group 2) Patients in the incentive group will demonstrate greater routinization compared to both the control group and the message group

For Aim 1, we will use these data to conduct descriptive analyses of rates of blood pressure control among patients with ambulatory care visits at Cedars-Sinai. Next, we will conduct multivariate regression models using blood pressure control as the outcome variable and various patient, physician and clinic characteristics as the independent variables. We will examine how results differ between the 2017 and JNC-7 guidelines.

For Aim 2, we will apply the new time-to-care measures and time-to-control measures to the same dataset. This will involve an iterative process of refinements as we discover issues that warrant the exclusion of certain blood pressure measurements, types of visits, or patient populations. The result will

be both refined measures and descriptive data on the time-to-care and time-to-control for both undiagnosed and uncontrolled hypertension.

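### Aim 1 measures control in all outpatients and leaves its rate denominators unstated, but its 20% and 50% benchmarks are shares of hypertensive people, and the 50% includes the undiagnosed

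*Protocol*

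**What the plan says.** - **Population.** The Protocol summary defines the subjects for Aims 1 to 3 as "All patients seen at least twice in a 12-month period at any Cedars-Sinai outpatient facility". The criteria in sections 3.2 and 3.3 and the data requirement in section 4.0 concern visits, age, setting and the presence of readings. None requires hypertension.
- **Control.** Section 4.0: "We will define blood pressure control based on the 2017 ACC/AHA guidelines (blood pressure <130/80". The definition does not depend on having hypertension.
- **Aim 1 analysis.** Section 7.1 describes "rates of blood pressure control among patients with ambulatory care visits at Cedars-Sinai". It then fits regression models "using blood pressure control as the outcome variable and various patient, physician and clinic characteristics as the independent variables".
- **Aim 1 objective.** Section 2.0 speaks of "cross-sectional prevalence of undiagnosed and uncontrolled hypertension within the Cedars-Sinai Health System".
- **Benchmarks.** Hypothesis 1 in section 7.1 says that the undiagnosed and uncontrolled rates "will be similar to national rates (20% and 50%, respectively". Section 1.0 gives the source of the 50%: "half of hypertensive individuals have blood pressures that exceed current standards for control". The same sentence counts the nearly 20% without a diagnosis as part of that half, and states that figure per hypertensive person too.
- **Numerators.** Section 4.0 defines undiagnosed hypertension as two readings at or above 130/80 with no diagnosis code in the preceding year. Uncontrolled hypertension uses the same readings but requires a code. Neither definition names a denominator.
- **SAP.** It covers the randomised pilot and says nothing about Aim 1.

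**The concern.** The only population written for the Aim 1 control analysis is all outpatients, and control is a property of the reading. Applied as written, a patient with normal blood pressure and no hypertension is a success in the control rate and in the regression. The benchmarks belong to a different population.

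Three results are at stake:
- **Hypothesis 1.** An all-patient rate could differ widely from 20% and 50% when care matches the national picture, or could agree with them when care is worse.
- **Hypothesis 3 and the regression.** The share of hypertensives that a clinic sees enters the result together with how well it controls them. The covariates in section 4.0 include comorbidities linked to hypertension, but not hypertension status.
- **Aim 3A.** If the same control rate is carried forward, the physician and clinic rates used to validate the new measures would partly reflect how few hypertensives a physician sees.

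There is also a mismatch that a change of denominator does not remove: the 50% counts the undiagnosed, and the plan's uncontrolled category leaves them out.

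**Working it through.** **Inputs**
- National rates among hypertensives: 20% undiagnosed and 50% above goal in total, the second including the first (sections 1.0 and 7.1).
- π, the share of Aim 1 patients who are hypertensive: not in the documents; varied from 0.3 to 1.0.
- For the clinic comparison, hypertensive shares π1 (the four named clinic types) and π2 (other clinics), and above-goal rates among hypertensives r1 and r2: not in the documents; assumed.

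The plan has no Aim 1 power calculation, test or similarity margin, so there is no calculation to reproduce. The two benchmarks can be traced to section 1.0, and they match it only with hypertensive people as the denominator.

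**Step 1. A system exactly at national rates, all patients as denominator.** Patients without hypertension enter the denominator only, so the all-patient rate is π × the rate among hypertensives. The last column uses 50% − 20% = 30% for coded, uncontrolled patients.

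| π | Undiagnosed (0.20π) | Above goal (0.50π) | Coded and uncontrolled (0.30π) |
|---|---|---|---|
| 0.30 | 6% | 15% | 9% |
| 0.45 | 9% | 22.5% | 13.5% |
| 0.60 | 12% | 30% | 18% |
| 0.80 | 16% | 40% | 24% |
| 1.00 | 20% | 50% | 30% |

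Only π = 1 returns 20% and 50%. Section 7.2 expects about 75,000 records. At 50%, the 95% half-width is 1.96 × √(0.5 × 0.5 / 75,000) = 0.0036, about 0.4 percentage points, so these gaps are not sampling noise.

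**Step 2. What it would take to observe the benchmarks.**
- To see 50% of all patients above goal, the rate among hypertensives must be 0.50/π. That exceeds 100% for π below 0.5, and is 83% at π = 0.6 and 62.5% at π = 0.8.
- To see 20% undiagnosed, it must be 0.20/π: 44% at π = 0.45, 33% at 0.6 and 25% at 0.8.

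Agreement with the benchmarks is therefore possible for some π, but it would mean worse care than the national figures.

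**Step 3. Clinic comparison.** Suppose that the named clinics control better, so r1 < r2. The all-patient rates are π1·r1 and π2·r2. The order reverses when π1·r1 > π2·r2, that is, when π1/π2 > r2/r1. All values below are assumed.
- 0.60 × 0.45 = 27% against 0.30 × 0.55 = 16.5%. Ratios 2.0 and 1.22: reversed.
- 0.70 × 0.45 = 31.5% against 0.40 × 0.60 = 24.0%. Ratios 1.75 and 1.33: reversed.
- 0.50 × 0.45 = 22.5% against 0.45 × 0.60 = 27.0%. Ratios 1.11 and 1.33: not reversed.

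**Step 4. After correcting the denominator alone.** Per hypertensive patient, a system at national rates shows 20% undiagnosed. Uncontrolled as defined in section 4.0 is 50% − 20% = 30% of all hypertensives. Among the diagnosed it is 30/(100 − 20) = 37.5%. Neither is 50%.

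**Step 5. Who may enter the control regression.** Under section 4.0 an uncoded patient is recognised as hypertensive only by having two readings at or above 130/80. In a control model for all hypertensives, such patients would be admitted because of the outcome, and their number would vary with each clinic's coding. A model limited to coded patients avoids this.

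**The case against.** The best defence is that this is an omission and not a decision. Section 7.1 nowhere says that normotensive patients count as controlled, or that the undiagnosed and uncontrolled rates are divided by all patients. Comparing them with benchmarks stated per hypertensive person suggests that hypertensive patients were meant. Section 4.0 promises a detailed study protocol that will specify eligibility, measures and analyses for Aims 1 to 3. The models adjust for age and hypertension-related comorbidities. Aim 1 is retrospective and preparatory, and the randomised comparison in Aim 4B does not depend on it.

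Much of this stands. The denominator of the two prevalence rates is unstated, and it would be wrong to report it as explicitly all patients. It does not dispose of the point. The control rate and the regression do have a written population, and it is not limited to hypertension. A promise of later detail does not supply a denominator, and adjustment for comorbidities does not condition on hypertension status.

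Three stronger readings are tempting, and the documents do not support them:
- **The benchmarks cannot be met.** This is true of the 50% only if fewer than half of the patients are hypertensive, and the documents do not give that share.
- **Hypothesis 1 would be rejected.** No test or margin for similarity is given, so rejection is undefined.
- **The clinic comparison will reverse.** It does so only if π1/π2 exceeds r2/r1. The documents contain no clinic-level prevalence, and one of the three examples above does not reverse.

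**Conclusion.** The concern holds in a limited form. As written, the Aim 1 control rate and regression mix the prevalence of hypertension with its control, and the undiagnosed and uncontrolled rates have no stated denominator although their benchmarks are per hypertensive person. If all patients are used, a system at national rates would show 6% to 12% undiagnosed and 15% to 30% above goal, on an assumed hypertensive share of 30% to 60%. Two analysts choosing different denominators would differ by a factor of 1/π. Reversal of the clinic comparison is a possibility under assumed inputs, not a prediction.

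The benchmark mismatch needs no assumption about π. It follows from sections 1.0 and 4.0: the 50% includes the undiagnosed, and the comparable figure for coded, uncontrolled hypertension is about 30% of hypertensives or 37.5% of the diagnosed, approximate because section 1.0 says nearly 20%.

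The change should be made, because hypotheses 1 and 3 of Aim 1 cannot be interpreted cleanly without it. The Aim 4B trial is unaffected.

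**What to change.** Amend the Aim 1 hypotheses and analysis text in Protocol section 7.1:

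1. Set the denominator for the undiagnosed rate and for the total above-goal rate to hypertensive patients: those with a hypertension code, or meeting the section 4.0 criterion for undiagnosed hypertension.
2. Compare the 50% with the total above goal (undiagnosed plus uncontrolled). Alternatively, restate the benchmark for coded uncontrolled hypertension as about 30% of hypertensives, or 37.5% of the diagnosed.
3. Fit the control regression, and the control part of the clinic comparison, in patients with a hypertension code. Analyse undiagnosed status separately among all hypertensives, so that uncoded patients do not enter the control model by virtue of being above goal.
4. Report all-patient prevalence as a descriptive figure only, with no benchmark.

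The cost is protocol wording and a filter in the analysis program. The regression will have fewer rows, and its result will speak for diagnosed patients only. No new data are needed.

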We will create three time-to-care measures: time-to-diagnosis, for patients who qualify for new diagnoses; time-to-initiate, for the same patients; and time-to-intensify, for patients with established diagnoses. We will create two time-to-control measures, one for patients with new and one for patients with established diagnoses. The new time-to-care and time-to-control measures will be based on the 2017 ACC/AHA guidelines. We will define undiagnosed hypertension as two ambulatory blood pressures \geq 130/80 without an ICD-9/10 code for hypertension in the preceding year; uncontrolled hypertension will be defined using the same blood pressure criterion but patients will have an ICD-9/10 code for hypertension. A new diagnosis of hypertension will be defined as an ICD-9/10 code for hypertension without a prior code or antihypertensive medication use in the preceding year. We will define treatment initiation as the first prescription for an antihypertensive medication following a new diagnosis of hypertension. Treatment intensification will represent the addition of another antihypertensive medication, an increase in the dose of an existing antihypertensive medication, and a change from one antihypertensive medication to another. We will access the 2017 guidelines and other standard sources to develop a list of antihypertensive medications. Time to care will be calculated as the number of days from the last blood pressure above goal to the documentation of the diagnosis or the initiation/intensification of treatment. Time to control will be calculated as the number of days from the last blood pressure above goal to the first blood pressure at goal.

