For Aim 3A, we will conduct unadjusted and then adjusted multivariate regression analyses assessing whether time-to-care and time-to-control measures are predictors of (i.e., associated with) blood pressure control rates at the physician level. We will perform these analyses at the physician and clinic levels because time-to-control rates are tautologically associated with the presence of control, and because many types of future quality improvement interventions would likely target individual physicians and clinics. We will compare performance on these measures and control rates between patients with visits in Primary Care, Internal Medicine, Nephrology, and Cardiology clinics than for patients who only receive care in other specialty and subspecialty clinics.

Next, we will perform interrupted time-series analyses of changes in the three hypertension measures after 2017 using multivariate regression models. These analyses will examine each hypertension measure (time-to-care, time-to-control, and control rates) as the dependent variable, using the quarter year as the independent variable. We will examine whether there is a change in intercept or slope during any quarter following the announcement of the ACC/AHA guidelines in 2017. We will then qualitatively compare such changes across the three outcome measures, to assess whether time-to-care is more responsive, as expected.

For Aim 3B, we will conduct unadjusted and then adjusted multivariate regression analyses assessing whether time-to-control measure was different between those enrolled in the pilot study and patients in the non-intervention group.

For Aim 4A, two independent coders will develop a codebook that details the inclusion and exclusion criteria, as well as typical exemplars for each topic or theme. Together, the coders will work to establish inter-coder reliability (evidenced by Cronbach's alpha $\geq .70$) with the goal to converge on a single, agreed upon meaning for each thematic area. For each topic, they will identify the range of themes mentioned, which were most and least salient, and which were discussed most and least frequently. This will produce research reports on specific topics describing the range, central tendency, and distribution of each theme, presenting segments of text as exemplars, which will be used to guide the refinement and implementation of the intervention in Aim 4B.

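### Averaging to physician or clinic level does not by itself remove the built-in link between time-to-control and control in the Aim 3A validity test

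*Protocol*

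**What the plan says.** Section 2.0 of the Protocol sets the validity criterion for Aim 3A: "we can examine whether performance on the new measures is associated with performance on cross-sectional measures of blood pressure control". Hypothesis 1 for Aim 3A in section 7.1 turns this into a test, with no size or benchmark: "Performance on the time-to-care and time-to-control measures will be associated with cross-sectional control rates at the clinic and physician level". The planned regressions ask whether the measures "are predictors of (i.e., associated with) blood pressure control rates at the physician level".

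Section 7.1 gives two reasons for the level of analysis. The first is the tautology: "We will perform these analyses at the physician and clinic levels because time-to-control rates are tautologically associated with the presence of control". The second is practical: "because many types of future quality improvement interventions would likely target individual physicians and clinics".

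Both quantities come from one source. For Aim 2, "we will apply the new time-to-care measures and time-to-control measures to the same dataset" as that used for the Aim 1 control rates. No split of patients, separate time window or null benchmark is described. The SAP covers only the randomised adherence trial and does not mention Aim 3A.

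The definition of time-to-control is not settled. Section 2.0 (Aim 2) describes how long the undiagnosed or uncontrolled state lasts until goal is reached. Section 4.0 instead counts the "number of days from the last blood pressure above goal to the first blood pressure at goal". Neither section says how patients who never reach goal are handled, and section 7.1 does not fix the denominator of the control rate.

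**The concern.** A patient whose pressure is usually above goal tends to wait longer for an at-goal reading and is also less likely to be at goal when control is assessed. That link arises from shared readings and says nothing about the quality of care. The plan sees this, and aggregation is the only answer it offers. But a physician's mean time-to-control and control rate are averages over overlapping patients and readings, so the link can pass straight into the averages.

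Association with cross-sectional control is the only validity test that section 2.0 names for these measures, and it says they are intended for future work. If shared readings alone can produce the association, a positive result does not separate validity from construction.

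**Working it through.** The documents give no expected correlation, power or number of physicians for this test, so there is no plan figure to reproduce.

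**Step 1. Identical physicians (algebra).** Let T be a patient's time-to-control, C the control status, and m the number of independent patients per physician.

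- Cov(mean T, mean C) = Cov(T, C)/m
- Var(mean T) = Var(T)/m and Var(mean C) = Var(C)/m
- The factor 1/m cancels, so Corr(mean T, mean C) = Corr(T, C) for any m.

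A simulation of correlated pairs agreed. Patient-level correlations of -0.1, -0.2, -0.3, -0.5 and -0.7 reappeared at physician level within about 0.015, with panels of 20 or 250. With 100 physicians, the share of tests significant at two-sided 0.05 was 16-17%, 50-51%, 84-89%, 100% and 100%.

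**Step 2. Physicians who differ.** Assume a within-physician correlation of -0.30, a true physician-level correlation of 0, and the same intraclass correlation (ICC) for both measures. Then

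r = -0.30 × [(1 - ICC)/m] / [ICC + (1 - ICC)/m]

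- ICC 0.05, m = 20: -0.30 × 0.0475/0.0975 = -0.15
- ICC 0.05, m = 200: -0.30 × 0.00475/0.05475 = -0.03
- ICC 0.02, m = 20: -0.30 × 0.049/0.069 = -0.21
- ICC 0.02, m = 200: -0.30 × 0.0049/0.0249 = -0.06

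Aggregation is thus a partial remedy, and its strength depends on two quantities that the plan does not give.

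**Step 3. Dependence on the definition.** Blood pressure was simulated with no physician effect: 200 physicians × 100 patients, 100 replicates. From the Protocol: goal below 130 systolic and two elevated readings to qualify. Assumed: systolic readings only, 12 visits about 90 days apart, mean 138, between-patient SD 12, within-patient SD 10, a modest downward trend, and visit gaps unrelated to pressure. Ranges run over three ways of measuring control: last reading, a mid-series reading, and share of readings at goal.

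| Time-to-control | Control-rate denominator | Physician-level r | Tests significant |
|---|---|---|---|
| From onset, never-controlled counted to end of follow-up | Same patients | -0.37 to -0.74 | 100% |
| From onset, never-controlled counted to end of follow-up | Whole panel | -0.27 to -0.41 | 99-100% |
| From onset, only patients who reach goal | Either | -0.04 to -0.44 | 13-100% |
| Literal section 4.0 wording | Either | about 0 | 4-6% |

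The last row is about zero because the literal wording reduces to the gap between two consecutive visits.

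**Step 4. Separate patients.** Time from onset, never-controlled counted to the end; time-to-control from one random half of each panel, control rate from the other.

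| Physicians × patients | True physician SD | Same patients: r (significant) | Split panels: r (significant) |
|---|---|---|---|
| 100 × 50 | 0 | -0.37 (98%) | -0.01 (7%) |
| 300 × 250 | 0 | -0.36 (100%) | +0.02 (3%) |
| 100 × 50 | 3 mmHg | -0.55 (100%) | -0.17 (44%) |
| 300 × 250 | 3 mmHg | -0.79 (100%) | -0.52 (100%) |

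Splitting brings the null close to its nominal 5% and still finds real differences, with a clear loss of power when panels are few and small.

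**The case against.** A reader might infer that aggregation leaves the link wholly intact and that the measures are bound to look valid. The documents do not support that.

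- The equality in step 1 is exact only when physicians are identical and both averages use the same patients. Step 2 shows real dilution where physicians differ, and the plan does not say that the control rate is restricted to patients with a time-to-control.
- The artefact depends on the definition. Under the literal section 4.0 wording it is absent. If only patients who reach goal are counted, even the sign is unstable: another set of assumed parameters gave +0.04 to +0.11, the wrong direction for validity and not significant with 200 physicians (p = 0.57 to 0.12).
- The Protocol never states that the tautology is avoided; it only offers the level of analysis as a response. Its second reason, that quality improvement targets physicians and clinics, justifies those levels independently.
- Hypothesis 3A.1 also covers three time-to-care measures, which the plan does not call tautological.
- Aim 3A is retrospective measure development with planned iterative refinement, and the randomised trial is untouched.

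All of this stands as a limit on the point, but none of it supplies the missing remedy. The literal section 4.0 reading conflicts with the duration described in section 2.0 and with the plan's own statement that a tautology exists. The quality-improvement rationale explains why one would aggregate, not how shared readings are dealt with.

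**Conclusion.** The point holds in a limited form. Physician- or clinic-level analysis is the plan's only answer to a tautology it acknowledges, and averaging alone does not guarantee its removal. Hypothesis 3A.1 could be supported for the two time-to-control measures without real validity if time-to-control is the duration of the uncontrolled state and never-controlled patients are carried or censored. Among identical physicians that definition passed the test in nearly every simulated run.

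The equality of correlations in step 1 rests only on independent, identically distributed patients. The simulated sizes rest on assumed blood pressure parameters and should not be read as predictions for this health system. The matter should be corrected before Aim 3A is analysed.

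**What to change.** In section 7.1 (Aim 3A):

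1. Delete the implication that aggregation deals with the tautology; keep the quality-improvement reason for the level of analysis.
2. Reconcile the section 2.0 and section 4.0 definitions of time-to-control. State how never-controlled patients are handled and which patients form the control-rate denominator.
3. Compute time-to-control in one random half of each physician's (and clinic's) patients and the control rate in the other half, relate the two across physicians and clinics, and average over repeated splits. A patient may see several physicians, so assign each patient to a half once per split. Splits are not independent, so take the standard error from resampling physicians.
4. Alternatively, keep the same-patient analysis but compare its association with the distribution obtained by randomly reassigning patients to physicians.

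The cost is one added analysis step on data already to be extracted. Physician-level figures become noisier because each rests on half a panel; averaging over splits recovers part of this, and section 7.2 expects at least 75,000 patients. Case mix shared by the two halves can still correlate them, so the planned covariate adjustment remains necessary.
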